#### **Research Procedure (Intervention group-VL/FIS)**

Following induction of general anesthesia and adequate manual ventilation, the anesthesia provider will attempt to successfully intubate the patient utilizing both, a video laryngoscope and a flexible intubation scope. No more than 2 intubation attempts shall be made. If necessary, between intubation attempts, adequate patient ventilation will occur before the next attempt.

For both the control and intervention groups, the anesthesia provider will be given the option to secure the airway via oral pathway (passage) according to clinical judgment. If a patient's airway has not been secured within the two attempts of the respective, allocation treatment, a third attempt will be made utilizing another technique or device (as a rescue attempt) at the discretion of the anesthesia provider. At this point, no further study data will be collected, except of what device was used for the rescue attempt and any potential Adverse Events.

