### **5.3 Measurements**

Morphometric characteristics and airway assessments of all patients will be recorded in the preoperative holding area. Patients will be asked questions to assess degree of irritation. Baseline measures of blood pressure, pulse, oxygen saturation, and End-Tidal CO2 will be recorded prior to induction. Vital signs will be recorded during preoxygenation, before induction of anesthesia, after induction of anesthesia, during laryngoscopy and/or bronchoscopy, after successful intubation, and 3 times while in recovery (at PACU arrival, at 30 and 60 minutes after PACU arrival). Lastly, we will ask the same questions to the patients about degree of irritation when they're fully awake. Additionally, the anesthesiologist will provide a personal, subjective assessment following successful or failed/rescue intubation with the corresponding research procedure/technique.

**Intubation technique:** Although the time required for successful intubation is not a primary endpoint for the study, the time and number of attempts required for successful tracheal intubation will be recorded for each patient. The glottis view obtained will be recorded using the percentage of glottis opening (POGO) score. If the epiglottis is down folded and a jaw lift is required to improve view, this information will be reported. The view both before and after jaw lift will also be recorded using the POGO score. If blood or secretions are present and require suctioning, time will be stopped while suctioning occurs and this will be recorded. If rotation of the ETT to obtain intubation is required or esophageal intubation occurs, this will also be recorded. The subjective level of difficulty in the performance of intubation will also be recorded.[2]

**Intubation:** We will record how long in seconds and number of attempts required for successful endotracheal intubation in each group. An attempt is defined as an attempt at placement of an ETT through the glottic opening, pass the vocal cords, and into the trachea. Removal/reinsertion of the laryngoscope/fiberoptic scope will constitute as a new attempt. If more than 2 attempts are needed or if the anesthesia provider discontinues protocol procedures, for any reason, the case will be deemed a failure.

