#### 5.4 Outcomes definitions

**Degree of difficulty:** Difficult ETT placement is the primary outcome defined as: (i.) either first intubation time >60 seconds or (ii.) first attempt failure at intubation or (iii.) ease of intubation reported as difficult by the provider dichotomized by a scale score of 4 or 5 versus 1, 2, or 3.

**Control group-FIS placement:** A successful attempt will be defined as when the insertion tip of the FIS enters the patient's mouth (or nose), leading to placement of the ETT into the trachea and confirmation of the end-tidal CO2 capnography waveform. Any other manipulation of the airway leading to incorrect placement of the ETT will be considered a failed attempt.

**Intervention group-VL/FIS placement:** A successful attempt will be defined as when the tip of the video laryngoscope blade and insertion tip of the FIS enters the patient's mouth, leading to placement of the ETT into the trachea and confirmation of the end-tidal CO2 capnography waveform. Any other manipulation of the airway leading to incorrect placement of the ETT will be considered a failed attempt.

**Difficult intubation:** The subjective level of difficult ETT insertion termed "Ease of Intubation" measured on a Likert scale from 1 to 5, with 1 being "Extremely Easy" and 5 being "Extremely Difficult."

**Ease of ETT insertion:** The subjective level of ease of ETT passage thought glottis (from 1 = *Extremely Easy* to 5 = *Unsuccessful*) in the performance of the randomized intubation technique (FIS vs VL/FIS) will be recorded.

**Incidence of desaturation:** Incidence of oxygen saturation  $\leq 92\%$  will be recorded.

**Degree of Irritation:** The subjective level of irritation provided by the patient (0 = *None*; 1= *Mild*; 2 = *Moderate*; 3 = *Severe*) perioperatively (both pre and post operatively) will be recorded.

**Total Time:** The total time from the beginning of either FIS or FIS/VL combination insertion until successful ETT intubation in seconds, as verified by capnographic waves, chest rise and fall, and fogging of the ETT will be recorded.

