## **10.2 Planned Statistical Analysis**

For the Secondary Objective:

To evaluate ease of use, each of the 3 dimensions described below will be assessed independently. First, the time of intubation will be assessed for distributional assumptions using histograms, stem and leaf plots, and box plots. Descriptive statistics such as the median and range or the geometric mean  $\pm$  SD will be used to summarize the data. Second, ordinal data describing the number of attempts will be summarized using the median and range; and third, the number of complications will be summarized using the median and range. For number attempts and complications, frequencies and percentages will be used if the maximum number is small ( $\leq$  4 attempts or complications). Comparisons between continuous covariates of interest will be conducted using a t-test, or Wilcoxon rank-sum test if more appropriate. Categorical covariates will be compared using chi-square or Fisher's exact test.

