## **10.3 Exploratory Analyses**

Depending on the distributional assessment of outcomes for each of the 3 items: i) time of intubation, ii) number of attempts, and iii) the number of complications, a total score will be derived for each patient. Each outcome will be translated into a binary scale. For example, starting with intubation time, the completion a procedure within 60 seconds will be assigned a '0', and completion taking more than 60 seconds will assign a '1'. For the number of attempts, we will assign a '0' for a single attempt and a '1' for more than a single attempt. And finally for complications, we will assign a '0' for no complication arising and a '1' for any complications arising. The total score will range from 0 to 3 and will be summarized using frequencies and percentages related to each level of the total score and using the mean score and standard deviation, whichever is more appropriate. Other exploratory outcomes include: Ease of ETT insertion (ranked on a 1 to 5 scale as described in Section 5.4) and will be summarized using descriptive statistics. These exploratory study outcomes will be compared between treatment arms using an independent samples t-tests or chi-square tests. Potential cut-points for these exploratory outcomes may be considered to inform if low versus high scores are associated with select patient outcomes of interest. Cumulative incidence plots will be used to visualize time to intubation, if appropriate. Multiple logistic regression analyses will be conducted to assess the association between any dichotomous outcomes of interest and type of intervention after adjusting for select covariates of interest.

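### Irritation is scored before and after surgery, but the generic tests in Section 10.2 ignore the preoperative score and, if chi-square or Fisher is used, the order of the grades

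*Combined protocol and SAP*

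**What the plan says.** Section 5.3 has patients questioned about irritation in the preoperative assessment and adds: "Lastly, we will ask the same questions to the patients about degree of irritation when they're fully awake". Section 5.4 lists Degree of Irritation among the outcome definitions as a patient-reported score with four ordered grades, 0 (none) to 3 (severe), which "perioperatively (both pre and post operatively) will be recorded". The word irritation appears nowhere else in the document.

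Section 10.2 is built around time of intubation, number of attempts and number of complications: "To evaluate ease of use, each of the 3 dimensions described below will be assessed independently". Two general sentences follow. One reads "Comparisons between continuous covariates of interest will be conducted using a t-test, or Wilcoxon rank-sum test if more appropriate"; the other assigns chi-square or Fisher's exact test to categorical variables. The Brief Analysis Plan in the Summary Table repeats this text.

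The only adjusted analysis is in Section 10.3, under exploratory analyses. It is a logistic regression for dichotomous outcomes, relating them to "type of intervention after adjusting for select covariates of interest". Those covariates are not listed.

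**The concern.** The trial collects a baseline value of an outcome, and the plan gives that value no use. The listed tests take no covariate. The plan also does not say whether a four-grade score counts as continuous (t-test or Wilcoxon) or categorical (chi-square or Fisher), and the second choice throws away the ordering.

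Preoperative symptoms are plausible here, because a history of head or neck radiation is one route to eligibility (Section 3.2). The documents give no rate for them. Where preoperative and postoperative scores are correlated, including the first as a covariate sharpens the comparison of the second at no extra data cost. Naming the method in advance also closes a choice that could otherwise be made after seeing the data.

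**Working it through.** **Plan's own figure.** The plan gives no power for irritation. Its only power statement is for the primary outcome (Section 10.1): 30% against 10%, 60 per arm, two-sided 0.05, 80%. With mean rate 0.20:

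(0.20·√60 − 1.96·√(2·0.20·0.80)) / √(0.30·0.70 + 0.10·0.90) = (1.549 − 1.109) / 0.548 = 0.804, giving power 78.9%.

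That agrees with the stated 80% to within rounding. It does not bear on irritation, except that 60 per arm and two-sided 5% are carried forward below.

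**Approximation treating the score as continuous.** Assume a difference of 0.5 SD and a pre-post correlation ρ. Relative to a postoperative-only comparison, baseline adjustment multiplies the variance by 1 − ρ².

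- Postoperative only: 0.5/√(2/60) − 1.96 = 2.739 − 1.96 = 0.779, power 78%.
- Adjusted, ρ = 0.3: 2.739/√0.91 − 1.96 = 0.911, power 82%.
- Adjusted, ρ = 0.5: 2.739/√0.75 − 1.96 = 1.202, power 89%.
- Adjusted, ρ = 0.7: 2.739/√0.51 − 1.96 = 1.875, power 97%.

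This overstates the gain for a coarse score on which many patients are at 0 beforehand, so the graded score was simulated directly.

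**Simulation of the graded score.** All inputs in this step other than 60 per arm and the 5% level are assumptions:

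- Preoperative and postoperative latent scores are bivariate normal, cut to grades 0-3, with symptomatic patients split 60/30/10 across grades 1/2/3.
- The arm shift is 0.5 SD, and 60% of controls are symptomatic after surgery.
- 10,000 trials were run per setting.

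Each cell shows power (%) of a tie-corrected Wilcoxon test on the postoperative score, then of a proportional-odds model with the preoperative score as covariate. The gain in points is in brackets, taken before rounding.

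| Symptomatic beforehand | ρ = 0 | ρ = 0.3 | ρ = 0.5 | ρ = 0.7 |
|---|---|---|---|---|
| 5% | 66.5, 66.3 (−0.2) | 66.6, 67.2 (0.5) | 66.3, 68.6 (2.3) | 65.8, 70.1 (4.3) |
| 10% | 65.7, 65.7 (0.0) | 67.0, 68.1 (1.1) | 65.4, 69.0 (3.7) | 66.0, 74.2 (8.2) |
| 30% | 66.5, 66.5 (0.0) | 66.6, 68.9 (2.2) | 66.3, 72.8 (6.5) | 65.8, 81.5 (15.7) |
| 50% | 65.7, 65.8 (0.1) | 67.0, 69.8 (2.8) | 65.4, 73.9 (8.5) | 66.2, 84.6 (18.4) |

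Here ρ is the latent correlation; the correlation of the observed grades is lower (for example 0.56 at latent 0.7 with 30% symptomatic beforehand). The Monte Carlo standard error is about 0.5 points on each power and 0.14-0.43 on the gain.

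**Validity.** With no arm effect, rejection was 4.7-5.2% for the postoperative Wilcoxon test and 5.0-5.5% for the adjusted model.

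**Cost of ignoring the order.** Under the same assumptions (2,000 trials per setting), a four-category chi-square test had about 46-51% power against 64-67% for Wilcoxon, a difference of roughly 15-20 points.

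**Fewer symptoms after surgery.** With 30% of controls symptomatic afterwards, a smaller run (600 trials per setting, likelihood-ratio test) gave adjusted against Wilcoxon power from 51.8 against 50.7 up to 68.7 against 53.3.

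**Fewer patients.** With 54 per arm, gains over the postoperative Wilcoxon test at the four values of ρ were −0.2 / 1.2 / 3.6 / 8.8 points (10% symptomatic beforehand) and −0.2 / 2.6 / 6.0 / 15.0 (30%).

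**The case against.** The strongest case against is that this is an efficiency preference on a measure that carries little weight. Irritation is not named in the primary, secondary or exploratory objectives. The nearest secondary objective covers hoarseness, soreness, dysphagia and injuries, and the documents never say that the 0-3 score is its measure. A reader might infer that a declared secondary endpoint has no analysis; the text does not go that far. This stands and limits the priority.

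The plan is also not closed to a sensible analysis. The generic sentences can be stretched to a Wilcoxon comparison of postoperative scores, which is valid. Section 10.3 could accommodate any-versus-no irritation adjusted for baseline. That is true, but it is optional, exploratory and limited to dichotomous outcomes with unnamed covariates.

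The gains are hypothetical, and the model can struggle with sparse grades. In a 2,000-trial run with 30% of controls symptomatic afterwards, 5% beforehand and ρ = 0.3, adjusted power was 45.6% against 49.4% for Wilcoxon. In that run 164 of 2,000 fits failed (8.2%) and were counted as non-rejections, which explains much of the shortfall. The objection does show that a fallback is needed.

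Finally, a reader might quote the much larger advantage of adjustment over a test on change from baseline. No section proposes a change score, so that comparison says nothing about this plan.

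**Conclusion.** The gap is real but small in consequence. The plan collects a paired, ordered score and offers only tests that ignore the first measurement and may ignore the order.

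It would be wrong to infer that the planned comparison is biased or invalid. Randomization protects an unadjusted comparison, and the primary endpoint, sample size and Type I error are untouched. What is lost is precision.

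Relative to a postoperative Wilcoxon test, adjustment is worth about 0-4 points of power when 5% are symptomatic beforehand, 0-8 at 10% and 0-18 at 30-50%. Large gains need both common preoperative symptoms and high correlation. At the lower prevalences, choosing an ordinal test over a four-category chi-square matters more, at about 15-20 points.

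These figures rest on an assumed 0.5 SD latent shift, 60% of controls symptomatic afterwards and 60 complete patients per arm. The documents give no irritation rates and no pre-post correlation. This is an optional, cheap improvement to a supportive outcome.

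**What to change.** Add to Section 10.2, and to the Brief Analysis Plan that repeats it: postoperative irritation (each item separately, if several are asked) will be compared between arms with a proportional-odds model that includes the corresponding preoperative score, tested by likelihood ratio. The proportional-odds assumption will be checked. If top grades are sparse they will be merged; if the model still does not converge, a Wilcoxon rank-sum test on the postoperative score will be used.

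The cost is wording, a little more analysis work and an assumption to check. Both scores are already collected.

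The fix leaves one matter open. Section 5.2 says that, once two attempts with the allocated technique have failed, "At this point, no further study data will be collected, except of what device was used for the rescue attempt" and adverse events. Postoperative irritation may therefore be missing for those patients, possibly unequally by arm, and a baseline covariate does not resolve that.

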## **10.3 Exploratory Analyses**

Depending on the distributional assessment of outcomes for each of the 3 items: i) time of intubation, ii) number of attempts, and iii) the number of complications, a total score will be derived for each patient. Each outcome will be translated into a binary scale. For example, starting with intubation time, the completion a procedure within 60 seconds will be assigned a '0', and completion taking more than 60 seconds will assign a '1'. For the number of attempts, we will assign a '0' for a single attempt and a '1' for more than a single attempt. And finally for complications, we will assign a '0' for no complication arising and a '1' for any complications arising. The total score will range from 0 to 3 and will be summarized using frequencies and percentages related to each level of the total score and using the mean score and standard deviation, whichever is more appropriate. Other exploratory outcomes include: Ease of ETT insertion (ranked on a 1 to 5 scale as described in Section 5.4) and will be summarized using descriptive statistics. These exploratory study outcomes will be compared between treatment arms using an independent samples t-tests or chi-square tests. Potential cut-points for these exploratory outcomes may be considered to inform if low versus high scores are associated with select patient outcomes of interest. Cumulative incidence plots will be used to visualize time to intubation, if appropriate. Multiple logistic regression analyses will be conducted to assess the association between any dichotomous outcomes of interest and type of intervention after adjusting for select covariates of interest.

## **11.0 DATA MONITORING**

All randomized studies conducted at MDACC are required to have a DSMB, unless noted otherwise.

### **11.1 Training of Clinical Site Personnel**

The training of clinical site personnel will be the responsibility of the PI. To ensure uniform data collection and protocol compliance, fully delegated study staff will review the investigational plan, techniques for the identification of eligible subjects, instructions on data collection, methods for soliciting data from alternate sources, and schedules for follow-up, as necessary, with the research coordinators.

### **11.2 Data Reporting**

All data will be recorded on the site's standard source documentation. The Investigator or designee is responsible for transferring the information to the appropriate Case Report Forms (CRFs) supplied by the Investigator. The Investigator is responsible for ensuring the forms are accurately completed at the time of, or as soon as possible after, the subject procedure or the availability of test results. The Investigator is required to sign the CRF on the appropriate page(s) to attest she has reviewed the recorded data.

### **11.3 Data Review**

The PI will review all CRFs for completeness and clarity upon receipt. Missing or unclear data will be requested as necessary throughout the study. The PI will request further documentation, such as physician procedure notes when UADEs and/or malfunctions are observed and reported. The Principal Investigator will permit inspection of the study files and subject CRFs by IRB representatives and/or responsible government agencies.

### **11.4 Data Management**

All of the study data will be collected on a paper case report form (CRF), which will be entered in a computer database. Each subject will be registered in OnCore and assigned a sequential number code. The key linking the code and the subject identifier will be kept in OnCore. The computer database will be password protected. All changes to the CRF will follow Good Clinical Practice guidelines. The Research Manager is responsible for auditing the consistency of the data transcribed from the paper CRF to the computer. A protocol violation log will be maintained, and all protocol violations will be reported to the IRB.

## **12.0 INVESTIGATOR REPORTS AND RESPONSIBILITIES**

Investigators are responsible for ensuring the investigation is conducted in accordance with the study protocol and applicable Federal regulations (21 CFR, Part 812, Subpart E). Investigators are also responsible for:

- Obtaining IRB approval for study conduct and re-approval as applicable (if more than one Investigator is participating in the study at a site, the Principal Investigator shall be responsible for the IRB approval and re-approvals)
- Obtaining informed consent of study subjects prior to enrollment into the clinical study
- Protecting the subject rights, safety, and welfare
- Maintenance of subject records and confidentiality
- Record retention as defined in Federal regulations 21 CFR, Part 812.140 (a), (d), and (e)

- Management of investigation and study related activities according to the Clinical Investigator Agreement and the Study Research Agreement
- Submission of site-specific study closure report to governing IRB within 3 months of notification from study Sponsor (if more than one Investigator is conducting the study, the Primary Investigator is responsible for submission of the study closure report)

In addition:

- An Investigator shall report to the Sponsor, within 5 working days, a withdrawal of approval by the reviewing IRB of the Investigator's part of an investigation
- If an Investigator uses a device without obtaining informed consent, the Investigator shall report such use to the Sponsor and the reviewing IRB within 5 working days after the use occurs
- An Investigator shall, upon request by a reviewing IRB or regulatory agency official, provide accurate, complete, and current information about any aspect of the investigation

### **13.0 TIMELINE FOR THE PROPOSED RESEARCH**

The timeline to completion of this study will be 12-72 months following IRB approval.

